1.1. Comparator Agent

Levetiracetam

Levetiracetam is indicated for use as an adjunctive therapy for POS (adults and children ≥ 1 month of age with epilepsy), PGTCs (adults and children ≥ 6 years of age with idiopathic generalized epilepsy), and myoclonic seizures (adults and children ≥ 12 years of age with juvenile myoclonic epilepsy [JME]).²⁴ The safety profile in pediatric subjects with epilepsy is summarized below.

Subjects With Partial-Onset Seizures

In pediatric subjects experiencing POS, levetiracetam is associated with somnolence, fatigue, and behavioral abnormalities.²⁴

In a double-blind, controlled study in children with epilepsy experiencing POS, 22.8% of levetiracetam-treated subjects experienced somnolence, compared with 11.3% of placebo subjects. The design of the study prevented accurately assessing dose-response effects. No subject discontinued treatment for somnolence. In about 3.0% of levetiracetam-treated subjects and in 3.1% of placebo subjects, the dosage was reduced as a result of somnolence.²⁴

Asthenia was reported in 8.9% of levetiracetam-treated subjects, compared with 3.1% of placebo subjects. No subject discontinued treatment for asthenia, but asthenia led to a dosage reduction in 3.0% of levetiracetam-treated subjects compared with 0% of placebo subjects.²⁴

A total of 37.6% of the levetiracetam-treated subjects experienced behavioral symptoms (reported as agitation, anxiety, apathy, depersonalization, depression, emotional lability, hostility, hyperkinesia, nervousness, neurosis, and personality disorder), compared with 18.6% of placebo subjects. Hostility was reported in 11.9% of levetiracetam-treated subjects, compared with 6.2% of placebo subjects. Nervousness was reported in 9.9% of levetiracetam-treated subjects, compared with 2.1% of placebo subjects. Depression was reported in 3.0% of levetiracetam-treated subjects, compared with 1.0% of placebo subjects.²⁴

A total of 3.0% of levetiracetam-treated subjects discontinued treatment due to psychotic and nonpsychotic adverse events, compared with 4.1% of placebo subjects. Overall, 10.9% of levetiracetam-treated subjects experienced behavioral symptoms associated with discontinuation or dosage reduction, compared with 6.2% of placebo subjects.²⁴

Subjects With Myoclonic Seizures

During clinical development, the number of subjects with myoclonic seizures exposed to levetiracetam was considerably smaller than the number with partial seizures. Therefore, underreporting of certain adverse events was more likely to occur in the myoclonic seizure population. In adult and adolescent subjects experiencing myoclonic seizures, levetiracetam is associated with somnolence and behavioral abnormalities. It is expected that the events seen in POS subjects would occur in patients with JME. In a double-blind, controlled study in adults and adolescents with JME experiencing myoclonic seizures, 11.7% of levetiracetam-treated subjects experienced somnolence compared with 1.7% of placebo subjects. In 1.7% of levetiracetam-treated subjects and in 0% of placebo subjects, the dosage was reduced as a result of somnolence.

Non-psychotic behavioral disorders (reported as aggression and irritability) occurred in 5% of the levetiracetam-treated JME subjects compared with 0% of placebo subjects. Non-psychotic mood disorders (reported as depressed mood, depression, and mood swings) occurred in 6.7% of levetiracetam-treated JME subjects compared with 3.3% of placebo subjects. A total of 5.0% of levetiracetam-treated subjects had a reduction in dosage or discontinued treatment due to behavioral or psychiatric events (reported as anxiety, depressed mood, depression, irritability, and nervousness), compared with 1.7% of placebo subjects.

In a well-controlled clinical study that included both adolescent (12 to 16 years of age) and adult subjects with myoclonic seizures, the most frequently reported adverse events associated with the use of adjunctive levetiracetam, not seen at an equivalent frequency among placebo-treated subjects, were somnolence, neck pain, and pharyngitis. The different pattern of adverse events, as compared with subjects with POS, is likely due to the much smaller number of subjects in the JME study.²⁴

Subjects With Primary Generalized Tonic-Clonic Seizures

During clinical development, the number of subjects 4 years of age and older with PGTCs exposed to levetiracetam was considerably smaller than the number with POS. As in the POS subjects, behavioral symptoms appeared to be associated with levetiracetam treatment. Gait disorders and somnolence were also described in the study in PGTCs, but with no difference between placebo and levetiracetam treatment groups and no appreciable discontinuations. Although it may be expected that drug-related events seen in POS subjects would be seen in PGTCs subjects (eg, somnolence and gait disturbance), these events may not have been observed because of the smaller sample size.²⁴

Discontinuation or Dosage Reduction in Well-Controlled Clinical Studies

The adverse events most commonly associated ($\geq 3\%$ in subjects receiving levetiracetam) with discontinuation or dosage reduction in the well-controlled pediatric POS study were asthenia, hostility, and somnolence. The adverse event most commonly associated ($\geq 3\%$ in subjects receiving levetiracetam) with discontinuation or dosage reduction in the well-controlled pediatric JME study was anxiety (2 subjects, 3.3%), but the small study size (a total of 113 subjects enrolled with JME) limits the conclusions that can be drawn. The PGTCs study was too small to adequately characterize the adverse events leading to discontinuation or dosage reduction.²⁴

Hematologic Abnormalities

Levetiracetam-treated pediatric subjects with POS experienced small, but statistically significant, decreases in white blood cell (WBC) and neutrophil counts and increases in lymphocyte counts, as compared with placebo. In a well-controlled study, more levetiracetam-treated pediatric subjects with POS had a possibly clinically significant abnormally low total WBC value (3.0%

levetiracetam-treated versus 0% placebo); however, there was no apparent difference between treatment groups with respect to neutrophil count. No subject was discontinued secondary to low WBC or neutrophil counts. Although there were no obvious hematologic abnormalities observed in subjects with JME, the limited number of subjects limits the conclusions that can be drawn.²⁴

Liver Function Test Abnormalities

There were no meaningful changes in mean LFT values in controlled studies in adult or pediatric subjects; LFT abnormalities were similar in drug- and placebo-treated subjects in controlled studies (1.4%). No pediatric subjects were discontinued from controlled studies due to LFT abnormalities.²⁴

Impaired Renal Function

Levetiracetam is known to be substantially excreted by the kidney, and the risk of adverse reactions to this drug may be greater in patients with impaired renal function.²⁴

Post-Marketing Experience With Adjunctive Therapy

The following have been reported in patients receiving marketed levetiracetam worldwide (alphabetical order): abnormal LFT values, choreoathetosis, dyskinesia, erythema multiforme, hepatic failure, hepatitis, leukopenia, neutropenia, pancreatitis, pancytopenia (with bone marrow suppression identified in some of these cases), Stevens-Johnson syndrome, thrombocytopenia, toxic epidermal necrolysis, and weight loss. Alopecia has been reported with levetiracetam use; recovery was observed in the majority of cases where levetiracetam was discontinued.

Levetiracetam Monotherapy

Levetiracetam is not approved as monotherapy for epilepsy; however, investigator-initiated studies of children with epilepsy support its use in this indication. These monotherapy studies used the same titration and maintenance dosing as pivotal adjunctive studies; overall efficacy and safety outcomes were similar in both treatment settings.^{21,24,29,43}

1.2. Overall Rationale for the Study

Among its various pharmacologic actions, topiramate is a carbonic anhydrase inhibitor and may induce metabolic acidosis, and other changes (eg, hypocitraturia, hypercalciuria, and elevated urine pH) that may be associated with an increased tendency for kidney stone formation.⁴¹ Chronic metabolic acidosis may be associated with abnormal bone mineralization and/or homeostasis of vitamin D, calcium, or phosphorus. Childhood is a critical period for bone mineralization and growth. The effects of topiramate on growth, bone mineralization, and kidney stone formation have not been fully and systematically evaluated or well characterized in pediatric populations.

Preclinical juvenile rat studies demonstrated various clinical chemistry and bone findings (eg, changes in serum and urinary phosphate, decreased global BMD, decreased growth plate thickness) with topiramate treatment that raise concerns about long-term toxicities in pediatric patients.

This study will systematically assess the long-term safety of topiramate monotherapy compared with levetiracetam monotherapy; specific emphasis will be on metabolic acidosis related to topiramate therapy and its association with nephrolithiasis, BMD abnormalities, and delayed growth in children (2 to 15 years of age).

2. OBJECTIVES AND HYPOTHESIS

2.1. Objectives

Primary Objective

The primary objective is to evaluate the effects of topiramate monotherapy compared with levetiracetam, another standard AED, as monotherapy for new-onset or recent-onset epilepsy on pediatric growth and maturation, bone mineralization, and kidney stone formation in children 2 to 15 years of age.

Secondary Objective

Overall safety will be assessed.

2.2. Hypothesis

The study will test the hypothesis that flexible dosages of topiramate monotherapy have the same effect as flexible dosages of levetiracetam monotherapy on pediatric growth, bone mineralization, and kidney stone formation in children 2 to 15 years of age with new-onset or recent-onset epilepsy, versus the alternative hypothesis that the effect of topiramate is different from that of levetiracetam.

3. STUDY DESIGN AND RATIONALE

3.1. Overview of Study Design

This is a 1-year, randomized, active-controlled, outpatient, multicenter, open-label, 2-arm flexible-dose monotherapy study of topiramate compared with 1 other AED (levetiracetam) in pediatric subjects with epilepsy. Subjects will be required to have newly or recently diagnosed epilepsy (within the previous 2 years, with at least 1, but no more than 10, unprovoked seizures during the 5 months prior to screening) characterized by POS with or without secondary generalization or PGTCS.

Approximately 282 male and female subjects, 2 to 15 years of age, with newly or recently diagnosed epilepsy, who meet the inclusion/exclusion criteria will be randomly assigned to either the topiramate or levetiracetam arm, in a 1:1 ratio. The randomization will be balanced using randomly permuted blocks and will be stratified by country and age group (2 to 5 years of age, 6 to 9 years of age, 10 to 12 years of age, and 13 to 15 years of age). The enrollment will be monitored throughout the study to ensure that subjects are enrolled for each integer year in each treatment group.

For each subject, his or her parent(s) (preferably both parents, if available) or a legally acceptable representative(s), as required by local regulations, must give written consent (permission) according to local requirements after the nature of the study has been fully explained and before the performance of any study-related activity. Children (minors) or subjects who are unable to comprehend the information provided can be enrolled only after obtaining consent from parents or a legally acceptable representative. Assent must be obtained from children (minors) capable of understanding the nature of the study, typically subjects 7 years of age and older, depending on the institutional policies. For the purposes of this study, all references to subjects who have provided informed assent/consent refers to the subject (assent as applicable) and his or her parent(s) or the subject's legal guardian(s) or legally acceptable representative(s) who have provided consent according to this process. Minors who assent to a study and later withdraw their assent should not be maintained in the study against their will, even if their parents still want them to participate.

The study will include the following 3 phases: a screening phase of up to 28 days, an open-label treatment phase of 1 year's duration, and a posttreatment phase of 30 days' duration. There may be an optional post-study follow-up phase to obtain dual energy x-ray absorptiometry (DEXA) measurements in a subgroup of subjects who experience a clinically important reduction (change in Z-score of -0.5 or greater) in BMD, based on local DEXA scan results, after 1 year of treatment with topiramate, to determine whether a decrease in BMD after or during 1 year of treatment with topiramate is reversible. These subjects will have a repeat DEXA scan 6 months after discontinuation of study drug.

To minimize any bias in measurement, after randomization 3 of the safety assessments will be obtained in a blinded fashion, including the DEXA scan, renal ultrasound, and height.

Screening Phase:

Subjects meeting the inclusion/exclusion criteria (see Section 4, Subject Selection) will be eligible to enter into the study. They (and/or their parents or legally acceptable representatives) will sign an informed consent/assent form as appropriate (see Section 16.2.3, Informed Consent) and enter a screening phase of up to 35 days. During the screening phase, subjects will be assessed for study

qualifications. Subjects (or their parents/guardians) will keep a seizure diary (date of seizure and description). Information will be transcribed onto the case report form (CRF). Seizure diaries will be maintained with the source documents.

Open-Label Treatment Phase:

Immediately following the Screening Phase, qualified subjects, based on inclusion/exclusion criteria, will be randomly assigned to 1 of 2 treatment groups during the open-label treatment phase: topiramate (up to 350 mg/day in subjects 2 to <10 years of age, and up to 400 mg/day in subjects 10 to 15 years of age) or levetiracetam (up to 60 mg/kg/day). Antiepileptic drug dosages may be adjusted for clinical effect (efficacy and safety) during the open-label treatment phase but may not exceed these maximum dosages.

Only AED monotherapy will be used for both treatment groups. However, subjects will not be discontinued from the study if 1 or more concomitant AEDs are added after initiating treatment with study drug. Data will be collected prior to the use of the concomitant AED(s) for the primary analysis. Data subsequently collected while on the concomitant AED(s) will be analyzed in a secondary analysis for each safety outcome of interest.

All subjects will enter a 30-day posttreatment phase after completing the open-label treatment phase.

The open-label treatment phase has 2 periods, titration and maintenance.

Titration Period

Randomization will take place on Day 1 (Visit 2). The Day 1 visit will serve as the baseline visit. All procedures on Day 1 (except dispensing of study drug) should be completed before randomization.

Study drug will be titrated as tolerated to the maximum recommended dosage for optimal clinical effect over approximately 6 to 8 weeks, based on titration guidelines according to clinical response (see Section 6, Dosage and Administration). For all subjects, at any time, up-titration of open-label study drug may be slowed down if clinically indicated for tolerability, and may be accelerated if clinically indicated for seizure control.

Subjects will return for a clinic visit at Month 1 and Month 2 for dispensing of study medication.

Maintenance Period

Subjects should be maintained on the dosage achieved at the end of the titration period through the remainder of the open-label treatment phase, with the option for dosage adjustment as required for optimal clinical effect. Changes to this schedule will be based on a risk-benefit assessment of the subject's clinical condition by the investigator.

Clinic visits will be scheduled at Months 1, 2, 3, 6, 9, and 12/early withdrawal. Extra visits may be scheduled at the discretion of the investigator. Blood samples for PK evaluations will be taken at Months 1, 3, 6, and 12/early withdrawal.

Posttreatment Phase

[figure not shown]
Subjects will be contacted by telephone 30 days after the last dose of study drug to monitor adverse events and concomitant medications. Subjects who complete the study or discontinue early from the study may, at the discretion of the investigator, either continue on commercially available topiramate or levetiracetam or taper off topiramate or levetiracetam over a period of up to 2 weeks during the posttreatment phase.

Post-Study Follow-up Phase

There may be an optional post-study follow-up phase to obtain DEXA measurements in a subgroup of subjects who experience a clinically important reduction (change in Z-score of -0.5 or greater) in BMD, based on local DEXA scan results, after 1 year of treatment with topiramate, to determine whether a decrease in BMD after or during 1 year of treatment with topiramate is reversible. These subjects will have a repeat DEXA scan 6 months after discontinuation of study drug. During study conduct, the sponsor will assess site/investigator interest for participation in this phase to determine if the follow-up phase will be included. An additional consent/assent will be required for this phase.

An external, independent Data Monitoring Committee (DMC) will be commissioned for this study. See Section 11.5, Data Monitoring Committee, for details.

A diagram of the study design is provided in [Figure 1](#).

Figure 1: Study Diagram

^a Optional post-study follow-up phase to obtain DEXA measurements in a subgroup of subjects who experience a clinically important reduction (change in Z-score of -0.5 or greater) in BMD, based on local DEXA scan results, after 1 year of treatment with topiramate; these subjects will have a repeat DEXA scan 6 months after discontinuation of study drug.

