Subjects must not have nephrocalcinosis, renal stones of any type, hydronephrosis, a history of long bone fractures, indwelling hardware, or abnormalities of the skeleton or spine. Subjects must not have congenital glaucoma, known ocular deficits, or clinically relevant abnormalities on renal ultrasound or DEXA scans. Subjects must not have a known history of disturbances of autonomic function, inborn errors of metabolism, mitochondrial dysfunction, or prior evidence of hyperammonemia. Subjects must not have any clinically significant abnormality in laboratory tests at screening, including a bicarbonate level <20 mEq/L, have a diagnosis of metabolic acidosis, or be on alkali therapy.

Caregivers of the subjects must be able to accurately maintain the subject take-home record and seizure diary.

DOSAGE AND ADMINISTRATION

Subjects will be randomly assigned to receive unblinded, flexible dosages of topiramate or levetiracetam as follows:

- Topiramate: weight-based dosing for subjects 2 to <10 years of age, not to exceed 350 mg/day, as tolerated; dosage for subjects 10 to 15 years of age not to exceed 400 mg/day, as tolerated
- Levetiracetam: weight-based dosing for all subjects 2 to 15 years of age, not to exceed 60 mg/kg/day, as tolerated. The maximum recommended daily dosage is 3,000 mg (1,500 mg BID).

Subjects will receive study drug in a twice-a-day regimen. After randomization, subjects will be titrated as tolerated to the maximum recommended dosage for optimal clinical effect over 6 to 8 weeks and will be maintained on that dosage through the open-label treatment phase, with the option for dosage adjustment as required for optimal clinical effect. Changes to this schedule will be based on a risk-benefit

assessment of the subject's clinical condition by the investigator. All study drugs will be provided in child-resistant packaging during the study.

Subjects are recommended not to exceed maximum recommended maintenance dosages; however, subjects will not be discontinued from the study if higher dosages are required for optimal clinical effect as judged by the investigator. Data collected while on dosages that exceed maximal recommendations may be analyzed separately, as appropriate.

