6. DOSAGE AND ADMINISTRATION

Subjects will be randomly assigned to receive unblinded, flexible dosages of topiramate or levetiracetam as follows:

- Topiramate: weight-based dosing for subjects 2 to <10 years of age, not to exceed 350 mg/day, as tolerated; not to exceed 400 mg/day in subjects 10 to 15 years of age, as tolerated
- Levetiracetam: weight-based dosing for all subjects 2 to 15 years of age, not to exceed 60 mg/kg/day, as tolerated

Subjects will receive study drug in a twice-a-day regimen (BID). The first dose of study drug on Day 1 will be taken in the evening. After randomization, subjects will be titrated as tolerated to the maximum recommended dosage for optimal clinical effect over 6 to 8 weeks and will be maintained on that dosage through the open-label treatment phase, with the option for dosage adjustment as required for optimal clinical effect. Changes to this schedule will be based on a risk-benefit assessment of the subject's clinical condition by the investigator.

Topiramate Titration in Subjects 2 to <10 Years of Age

Dosing in subjects 2 to <10 years of age is based on weight. During the titration period, the initial dosage of topiramate should be 25 mg/day, administered nightly for the first week. Based upon tolerability, the dosage can be increased to 50 mg/day (25 mg BID) in the second week (see Tables 1 to 3 in the titration schedules in [Attachment 2](#)). Dosage can be increased by 25 to 50 mg/day each subsequent week as tolerated. Titration to the maximum recommended dosage should be attempted over 6 to 8 weeks. Based upon tolerability and seizure control, the rate of titration may be adjusted to achieve optimal clinical response. The total daily dosage should not exceed the maximum maintenance dosage for each range of body weight ([Table 1](#)). Subjects with a body weight >38 kg will be assigned to the titration schedule for subjects 10 to 15 years of age, as described below.

Table 1: Topiramate Monotherapy Target Total Daily Maintenance Dosing for Subjects 2 to <10 Years of Age

Weight (kg)	Total Daily Dosage (mg/day) ^a	
	Minimum Maintenance Dosage	Maximum Maintenance Dosage
Up to 11	150	250
12 – 22	200	300
23 – 31	200	350
32 – 38	250	350

^a Administered in 2 equally divided doses.

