meals. Study staff will instruct subjects and/or parents/caregivers on how to store medication for at-home use as indicated for this study. If a subject vomits within 30 minutes of receiving a dose, the dose will be repeated. If a subject vomits a second time or more than 1 hour later, the dose will not be repeated. All cases of vomited doses and action taken must be recorded in the subject's take-home record. Subjects will be instructed to take any missed doses of study drug as soon as possible. However, if the subject is within 6 hours of taking the next scheduled dose, he or she should wait until then to take the usual dose of study drug and skip the missed dose. Subjects should not take a double dose in case of a missed dose.

Subjects should be titrated and maintained according to clinical response, eg, titration may be slowed on the basis of tolerability and may be accelerated for the purposes of seizure control. Maintenance dosages should be based on optimal clinical response and may be adjusted at any time during the open-label treatment phase. Subjects are recommended not to exceed maximum recommended maintenance dosages; however, subjects will not be discontinued from the study if higher doses are required for optimal clinical effect as judged by the investigator. Data collected while on dosages that exceed maximal recommendations may be analyzed separately, as appropriate.

Once a subject completes the study or discontinues early from the study, at the discretion of the investigator, he or she will either continue on commercially available topiramate or levetiracetam or be tapered off of topiramate or levetiracetam over a period of up to 2 weeks.

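### The topiramate maximum is stated inconsistently, by age and weight and in its force, so above-maximum dosing is not uniquely defined and the SAP 5.4 cap does not match the dosing rules

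*Protocol*

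**What the plan says.** **Size of the maximum.** Under Dosage and Administration, the synopsis gives "Topiramate: weight-based dosing for subjects 2 to <10 years of age, not to exceed 350 mg/day, as tolerated". The first bullet of Section 6 repeats it: "weight-based dosing for subjects 2 to <10 years of age, not to exceed 350 mg/day, as tolerated". Section 3.1 states the same 350 mg/day for ages 2 to <10, and 400 mg/day for ages 10 to 15. None of the three mentions an exception by weight.

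The Section 6 text on titration in the younger group adds a limit by weight band: "The total daily dosage should not exceed the maximum maintenance dosage for each range of body weight". Table 1 in that section gives maxima of 250, 300, 350 and 350 mg/day, and its last band ends at 38 kg. For heavier children the text reads: "Subjects with a body weight >38 kg will be assigned to the titration schedule for subjects 10 to 15 years of age". That schedule is Table 4 of Attachment 2.

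**Force of the maximum.** Section 3.1 says dosages may be adjusted "but may not exceed these maximum dosages". This sentence covers levetiracetam as well. The synopsis and the end of Section 6 only advise against going above the maxima. Section 6 adds: "subjects will not be discontinued from the study if higher doses are required for optimal clinical effect as judged by the investigator". Both places allow data collected above the maxima to be analysed separately, as an option.

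**SAP.** Section 5.4 deals with overlapping exposure records. Where the summed topiramate dose is above what the subject is allowed, it is replaced by 350 mg (under 10 years) or 400 mg (10 years and over). Section 5.1 takes age at the date of dosing. Section 5.5 lists wrong treatment or dose deviation as a major deviation category and gives no threshold.

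**The concern.** A child under 10 who weighs more than 38 kg can go above the age-based maximum simply by following the schedule that Section 6 assigns. No investigator decision to go higher is needed. For children of any age or weight, the protocol also leaves unclear whether the maximum is a limit or advice.

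The statistical consequence is that the class of above-maximum exposure depends on which passage the analyst reads. This touches three things: which records count as dose deviations, which data would enter the optional separate analysis, and how overlapping exposure records are reset. Exposure matters here because the primary objective concerns growth, bone mineralization and kidney stones. The rationale recorded for Amendment INT-3 says that higher doses could confound DEXA scans, laboratory tests such as bicarbonate, and renal ultrasounds.

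**Working it through.** No power or sample-size figure is involved. The check sums the morning and evening doses at the last step of each topiramate schedule in Attachment 2 and compares them with the stated maxima.

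**1. Reproduce the plan's own figures.**
- Table 1 (up to 11 kg): 100 + 150 = 250 mg/day.
- Table 2 (12 to 22 kg): 150 + 150 = 300 mg/day.
- Table 3 (23 to 38 kg): 175 + 175 = 350 mg/day.

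All three agree with Table 1 in Section 6, and Table 3 reproduces the 350 mg/day stated for ages 2 to <10.

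**2. Children under 10 above 38 kg.** Attachment 2 Table 4, week 6: 200 + 200 = 400 mg/day. Against the age-based figure, 400 − 350 = 50 mg/day, and 50/350 = 14.3%.

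**3. Compare with the SAP 5.4 replacement value for a child under 10 (mg/day).**

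| Weight | Last step of assigned schedule | Overall figure for age <10 | SAP 5.4 value |
|---|---|---|---|
| up to 11 kg | 250 | 350 | 350 |
| 12 to 22 kg | 300 | 350 | 350 |
| 23 to 38 kg | 350 | 350 | 350 |
| above 38 kg | 400 | 350 | 350 |

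In the first two rows the protocol does not contradict itself, because 350 can stand as an overall ceiling above tighter weight-band maxima. The mismatch there is in the SAP, which uses 350 as the only value. In the last row the protocol contradicts itself and the SAP follows one side.

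**4. Follow SAP 5.4 as written, for overlapping records only.**
- Above 38 kg: a summed dose of 400 mg is reset to 350 if the allowed maximum is read by age. If it is read as 400, only sums above 400 trigger the rule, but they are still reset to 350, below the last step of the assigned schedule.
- Up to 11 kg: if the allowed maximum is read as 250, a sum between 250 and 350 triggers the rule and is raised to 350. If it is read by age, the same sum is left alone.
- 12 to 22 kg: the same happens for sums between 300 and 350.

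**5. Force.** The dosing bullets and Section 3.1 are worded as limits. The titration text in Section 6 uses weaker wording ("The total daily dosage should not exceed the maximum maintenance dosage for each range of body weight"). The synopsis and the end of Section 6 give a recommendation. One maximum cannot be both a limit and advice.

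**The case against.** The strongest reply has four parts.

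**The rule above 38 kg is a specific exception.** Table 1 in Section 6 stops at 38 kg, and the sentence beside it says where heavier children go. That is a fair reading of intent. However, the general statements in the synopsis, Section 3.1 and the Section 6 bullet do not mention the exception, and SAP 5.4 does not apply it.

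**Keeping a subject in the study is not permission.** A reader might infer that Section 6 authorises higher doses. It does not say so: it advises against them and says such subjects are not discontinued. The protocol handles added antiepileptic drugs in the same way. This narrows the conflict to one of force, but advice not to exceed still differs from "but may not exceed these maximum dosages".

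**The consequences are easily overstated.**
- A reader might infer that the separate analysis cannot be defined. The protocol makes it optional, the SAP does not include it, and SAP 5.4 does state numerical maxima. The accurate statement is that the class is not uniquely defined.
- A reader might infer that the same child would be compliant at one site and a major deviation at another. SAP 5.5 gives no dose threshold and does not say that sites classify deviations, so this is not supported.

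**The 14.3% is not a dose received.** A reader might apply it to every child under 10 above 38 kg. It compares a schedule endpoint with a stated maximum, while dosing is flexible and as tolerated. Nor does it measure relative exposure by weight: 400/38 = 10.5 mg/kg/day at the 38 kg boundary, against 350/23 = 15.2 and 250/11 = 22.7 from Table 1. These figures do not bear on which limit is right. Inclusion criterion 3 also restricts screening weight to the 5th to 95th percentile for age, which narrows the group.

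In addition, SAP Section 1 records that enrolment has stopped, and SAP Section 7 plans no formal testing. A protocol clarification alone would therefore change little now.

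**Conclusion.** Two inconsistencies stand in the current protocol text. The 350 mg/day stated for ages 2 to <10 conflicts with the assignment of children above 38 kg to a schedule ending at 400 mg/day, a gap of 50 mg/day if the last step is reached. The wording of Section 3.1 conflicts in force with that of the synopsis and the end of Section 6.

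As a result, above-maximum exposure is not uniquely defined for dose deviations or for the optional separate analysis. The age-only value in SAP 5.4 matches neither the rule above 38 kg nor the 250 and 300 mg/day weight-band maxima.

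The practical effect is probably limited. The SAP 5.4 mismatch affects only overlapping exposure records. The number of children under 10 above 38 kg is not in the documents and may be small. No primary result is shown to depend on the point. It is worth correcting because SAP 5.4, followed as written, can record a value that differs from the assigned schedule, and the correction is cheap.

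**What to change.** 1. Reconcile the synopsis, Section 3.1, Section 6 (bullets, titration text, Table 1 and closing paragraph) and Attachment 2 to one statement of the topiramate maximum by age and weight. State once whether that maximum, and the levetiracetam maximum covered by the same sentence in Section 3.1, may be exceeded. Both choices belong to the sponsor's clinical team.
2. Put the reconciled maximum in the SAP as one definition by age and weight. Say which weight applies: SAP 5.4 already uses weight at the start of the titration and maintenance periods for the mg/kg summary.
3. Use that definition in the SAP 5.4 rule, both to trigger it and as the replacement value. Use it also in classifying dose deviations under SAP 5.5 and in any flag for above-maximum data.
4. Report how many children under 10 weighed more than 38 kg, and how many exposure records the rule changed.

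The cost is one protocol clarification and one SAP definition with its programming. Dose, age and weight are already collected. With enrolment stopped, the SAP definition is the more useful part.
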